14.2 Statistical Analysis Plan

This is a Phase 1 open-label, multi-center clinical trial. Descriptive statistics will be employed to evaluate the safety and tolerance of ADXS11-001. Summary statistics for continuous variables will include mean, standard deviation, median and range. Categorical variables will be presented as frequency counts and percentages; and time-to-event variables will be summarized by Kaplan-Meier medians and survival plots. Data listings will be created to support tables and present data. The safety analysis will be performed on the safety population. The efficacy analysis will be performed on the efficacy population. SAS 9.2 or higher will be used for data analysis.

The data will be tabulated and analyzed with respect to subject enrollment and disposition, demographic, and baseline characteristics.

14.3 Sample Size

- The dose escalation portion of the study will enroll between 6-12 subjects based on observed AEs and/or DLTs within the dose cohorts.
- Additional subjects may be enrolled in an expansion cohort of the highest dose level to allow approximately 15 subjects to be treated at that dose level.

14.4 Treatment Randomization and Blinding

This is an open-label, multi-center trial. No placebo or active control is used and therefore no randomization is involved.

14.5 Study Populations

All subjects who receive at least 1 dose of study treatment will be included in the safety analyses. All subjects who complete at least 1 cycle of ADXS11-001 treatment will be included in the efficacy population.

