Sponsor:	Name of Finished Product:	Type of Treatment:
Advaxis, Inc.	ADXS11-001	Lm-LLO Immunotherapy

- Subjects who have undergone a major surgery or who have a new artificial implant and/or medical device which meets eligibility criteria must have a minimum 6-week time period elapsed from the time of surgery to the initiation of study treatment.
- Subjects who are receiving or are expected to receive future treatment with PI3K or TNFα inhibitors.

Test Product, Dose, Mode of Administration:

ADXS11-001 is a live attenuated bioengineered strain of Listeria monocytogenes (Lm)-LLO.

Reference Therapy:

None

Study Duration:

Each subject will participate in the trial for up to 5 years from the time the subject signs informed consent through the final study contact. The study duration includes an active study treatment phase (~24 months) and a 3-year *Lm* surveillance monitoring period, which includes 6 months of oral antibiotic administration to commence upon completion of the active study treatment phase or upon study discontinuation.

Criteria for Evaluation:

Safety: Recorded AEs; physical examinations, including vital sign measurements; clinical laboratory evaluations; *Lm* surveillance blood cultures

Efficacy: Tumor response and progression free survival (PFS)

Immunologic effects: Collection and analysis of peripheral blood

Statistical Methods:

Descriptive statistics will be used to summarize and evaluate the outcomes.

Demographic and baseline subject characteristics will be summarized. AEs will be classified and summarized by type, incidence, severity, and causality. All AEs will be summarized by subject, dose level, and prior recurrence history (aggressive/non-aggressive). All subjects who received at least 1 dose of ADXS11-001 will be included in the safety analyses.

Disease response will be tabulated for all subjects who receive ADXS11-001. PFS is defined as the time from first dose of study treatment until objective tumor progression or death. Subjects who have not progressed or who are still alive at the time of evaluation will be censored for the analysis. Kaplan-Meier curves and descriptive statistics will be used to summarize PFS.

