6 STUDY DESIGN AND TREATMENT PLAN

In this Phase 1, open-label, multi-center study, subjects with persistent, metastatic or recurrent squamous cell or non-squamous cell carcinoma, adenosquamous carcinoma, or adenocarcinoma of the cervix who have failed conventional therapy will receive the highest dose tolerated of ADXS11-001 infused intravenously (IV)

(± 10 minutes) with overall infusion volume of 250 mL on Day 1 of Weeks 1, 4, 7, and 10 of each 12-week cycle. Subjects must complete the prophylactic regimen at least prior to each ADXS11-001 infusion (as noted in Section 11.1) to mitigate and manage the potential immune response seen with immunotherapy administration.

Subjects who experience a DLT during the dose escalation portion of the study or experience events described as a DLT in any subsequent treatment cycle will be discontinued from study treatment. However, if the subject who experienced a DLT shows significant response to ADXS11-001, they may be eligible to receive ADXS11-001 at a lower dose level for subsequent doses and cycles following discussion and agreement between the Investigator and Sponsor. See Section 6.1 Dose Limiting Toxicity Criteria for definition of DLT.

The treatment to be used in this trial is outlined below in Table 4. Trial treatment should begin on the day of randomization or as close as possible to the date on which the treatment level is allocated/assigned.

Details on the dose calculation, preparation and administration are provided in the Pharmacy Manual.

Table 4 Trial Treatment

[figure not shown]
Dose Level	ADX11-001	Schedule
1	5 x 10 ⁹ CFU	Q3wks
2	$1 \times 10^{10} \text{CFU}$	Q3wks
-1	$1 \times 10^9 \text{CFU}$	Q3wks

ADXS11-001 will be given as a 3 weeks in repeating 12-week cycles

250 mL IV infusion every

A standard 3 + 3 design will be used in the dose escalation portion of the study. ADXS11-001 will be administered in sequential cohorts of 3-6 subjects, with a minimum of 48 hours between initial dosing for each of the first 3 subjects treated at each dose level. The first cohort will enroll a minimum of 3 subjects, according to a standard 3 + 3 design shown schematically in Figure 1.

Figure 1 3+3 Design Schematic

- Subjects in the first cohort will receive a dose of ADXS11-001 5 x 10⁹ CFU (Dose Level 1).
- If no DLTs are experienced in the 28 day DLT observation period at Dose Level 1, the next dose level of ADXS11-001 1 x 10¹⁰ CFU (Dose Level 2) will be explored.

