- Baseline tumor imaging and assessments must be performed within 28 days prior to the first ADXS11-001 infusion in the first study cycle. Subsequent tumor imaging and assessments will be conducted at Week 12 (±1 week) for the duration of study participation. Apparent progression within the first 12 weeks, not accompanied by clinical deterioration, should be confirmed ≥4 weeks later.
- Immune monitoring/T-cell samples will be collected immediately prior to each ADXS11-001 infusion (Day 1 of Weeks 1, 4, 7, and 10) and between 11-14 days after every ADXS11-001 infusion in Cycle 1 only.
- Cytokine samples will be collected **in Cycle 1 only** at 3 time points immediately prior to each ADXS11-001 infusion and 2 hours and 4 hours post infusion (±15 minutes- Day 1 of Weeks 1, 4, 7, and 10).

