9.1.2 Tumor Imaging and Assessment of Disease

Computed tomography (CT) and magnetic resonance imaging (MRI) will be considered the best currently available and reproducible methods to measure target lesions (as

defined in Section 9.1.4, Definition of Target/Non-target Lesions) selected for response assessment. Conventional CT should be performed with contiguous cuts of 10 mm or less. Spiral CT scan should be performed using a 5 mm contiguous reconstruction algorithm (as a general rule, lesion diameter should be no less than double the slice thickness). Lesions on chest x-rays will be acceptable as measurable lesions when they are clearly defined and surrounded by aerated lung; however, CT is preferable. Ultrasound is not an acceptable method to measure disease.

Assessment of disease will be done using both RECIST 1.1 criteria and irRECIST criteria. All subjects who have completed one 12-week cycle of ADXS11-001 treatment will be considered evaluable for response.

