14.5.5 Analysis of Efficacy

All subjects who complete at least one cycle of ADXS11-001 treatment will be included in the efficacy analyses. The following are efficacy parameters for the study:

- 1. Objective Response Rate (ORR)
- 2. Duration of tumor response
- 3. Stable Disease Rate (proportion of CR, PR, SD)
- 4. Duration of Stable Disease (SD)
- 5. Progression free survival (PFS)

Tumor response will be evaluated by RECIST 1.1 and irRECIST criteria. The ORR will be calculated as the proportion of subjects who achieved CR/irCR or PR/irPR. The duration of response is defined as the time interval from CR/irCR or PR/irPR to disease progression or death. If the subject's disease remains responsive by the time of discontinuation or completion of the study, the duration will be censored at that time point. The stable disease rate will be calculated as the proportion of subjects who achieved CR/irCR, PR/irPR or SD/irSD. The duration of SD is defined as the time interval from CR/irCR or PR/irPR or SD/irSD to disease progression or death. If the subject's disease remains stable by the time of discontinuation or completion of the study, the duration will be censored at that time point.

PFS is defined as the time interval from first infusion of study treatment to disease progression or death. If the subject's disease has not progressed by the time of discontinuation or completion of the study, the PFS will be censored at that time point.

Efficacy parameters will be descriptively summarized by dose cohorts as well as for all cohorts combined. Tumor response will be summarized according to response category. Response rate and stable disease rate will be summarized by frequency table. For durations of response and SD/irSD as well as PFS, the Kaplan-Meier method will be used to estimate the median times. Descriptive statistics and Kaplan-Meier curves will be presented.

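### Limiting efficacy to subjects who complete a 12-week cycle biases response rates and PFS upward and conflicts with the Synopsis

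*Combined protocol and SAP*

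**What the plan says.** Three sections restrict efficacy to completers. Section 14.5 defines the set: "All subjects who complete at least 1 cycle of ADXS11-001 treatment will be included in the efficacy population". Section 14.5.5 repeats it for ORR, duration of response, stable disease rate, duration of stable disease and PFS: "All subjects who complete at least one cycle of ADXS11-001 treatment will be included in the efficacy analyses". Section 9.1.2 does the same for response: "All subjects who have completed one 12-week cycle of ADXS11-001 treatment will be considered evaluable for response".

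The Synopsis, under Statistical Methods, differs: "Disease response will be tabulated for all subjects who receive ADXS11-001". Its PFS text contains no completer restriction.

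Other provisions that bear on the point:

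- Infusions are given "on Day 1 of Weeks 1, 4, 7, and 10 of each 12-week cycle" (Section 6).
- The imaging footnote to Table 5 reads: "Subsequent tumor imaging and assessments will be conducted at Week 12 (±1 week) for the duration of study participation".
- Section 14.5.5 defines the response rate: "The ORR will be calculated as the proportion of subjects who achieved CR/irCR or PR/irPR". It counts PFS from the first infusion to progression or death, and censors subjects without progression at discontinuation or study completion.
- Under Sections 6 and 11.6.2, subjects with a DLT during escalation, or who "experience events described as a DLT in any subsequent treatment cycle will be discontinued from study treatment", come off treatment. A subject showing significant response may continue at a lower dose level by agreement.

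No section says whether completing a cycle means receiving four infusions or reaching Week 12. No sensitivity analysis in all treated subjects is specified.

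**The concern.** Membership of the efficacy set depends on what happens after treatment starts. A subject who dies, deteriorates, has a limiting toxicity or withdraws during the first cycle is removed from the denominator, and such subjects are rarely responders. The rates then describe women who got through the first cycle, not women who were given the drug.

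PFS has a related defect. The clock starts at first infusion, but entry to the analysis requires finishing the cycle, so early deaths and stops for clinical deterioration cannot contribute events.

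The Synopsis and Section 14 also lead to different response rates from the same data. The expansion cohort is meant to describe clinical activity as well as safety at the RP2D, in about 15 subjects, so each exclusion visibly moves the estimate.

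**Working it through.** **The plan's own figure.** The only sample-size figure that can be reproduced is the escalation range in Section 14.3. Two dose levels visited with 3 or 6 subjects each give 6, 9 or 12, which matches 6-12. The documents give no expected ORR, PFS or drop-out rate, so the values of r, k, m and s below are assumptions shown over a range.

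**Who leaves and who stays.**

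- *Leaves:* subjects who die, or who stop before the cycle ends for clinical deterioration, toxicity or withdrawal. No scan is scheduled before Week 12. Table 5 marks imaging at end of therapy, but Section 8.4 makes it conditional. Most of these subjects will therefore have no documented response, and a progression that is documented is dropped with the subject.
- *Leaves, with a response-dependent exception:* subjects with a DLT. Only those judged to show significant response may continue, so the rule tends to keep responders and lose non-responders.
- *Stays:* a subject whose tumour grows silently and is found at the Week 12 scan, after the Week 10 infusion. The footnote to Table 6 and Sections 9.1.11 and 9.1.12 also keep early progressors without rapid clinical deterioration on treatment pending confirmation.

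**Response rates.** Let n be the number treated, r the responders and k the non-completers without a documented response. All treated: r/n. Completers: r/(n-k). The ratio is n/(n-k) = 1/(1-q), with q = k/n. With n = 15:

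| r | All treated | k = 1 | k = 3 | k = 5 |
|---|---|---|---|---|
| 2 | 13.3% | 14.3% | 16.7% | 20.0% |
| 3 | 20.0% | 21.4% | 25.0% | 30.0% |

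For r = 3 the exact 95% intervals are 4.3-48.1% (3/15), 5.5-57.2% (3/12) and 6.7-65.2% (3/10). The factor is 1.11, 1.25, 1.43 and 1.67 for q = 10%, 20%, 30% and 40%. The stable disease rate behaves the same way for non-completers with no assessment. The factor is a maximum: a non-completer with a favourable unscheduled or end-of-therapy scan reduces it.

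**PFS.** Assume exponential PFS with true median m weeks, F(t) = 1 - 2^(-t/m), and let a share s of the events before Week 12 be excluded. The retained fraction is N = 1 - s·F(12). Survival among those retained is [1 - F(t) - s(F(12) - F(t))]/N before Week 12 and [1 - F(t)]/N afterwards.

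Example, m = 12: F(12) = 0.5. With s = 0.5, N = 0.75; setting 2^(-t/12) = 0.5 × 0.75 = 0.375 gives t = 17.0 weeks. With s = 1, N = 0.5, and 2^(-t/12) = 0.25 gives t = 24 weeks.

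| True median (weeks) | s = 0.25 | s = 0.5 | s = 1 |
|---|---|---|---|
| 8 | 9.4 | 12.5 | 20 |
| 12 | 14.3 | 17.0 | 24 |
| 16 | 18.5 | 21.2 | 28 |
| 20 | 22.6 | 25.4 | 32 |
| 26 | 28.7 | 31.5 | 38 |

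The rise is 1.4 to 2.7 weeks at s = 0.25, 4.5 to 5.5 weeks at s = 0.5, and 12 weeks at s = 1.

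**The case against.** The strongest reply is that the rule removes less than it seems to. A reader might infer that the first 12 weeks are free of events by construction, and that the median is inflated by the full 12 weeks. The documents do not support that. Most radiologic progression in that window would be recorded at the Week 12 scan in subjects who finished the cycle, and early progression without rapid deterioration does not end treatment. Eligibility also screens out rapidly progressing disease, life expectancy under 6 months and expected inability to receive one cycle. This stands as a limit on size. It does not remove the bias, because those criteria are predictions and deaths and clinical stops are still lost.

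A second tempting inference is that every DLT subject is lost and that this inflates PFS. Neither part holds as stated. The exception can keep some of them. One who stops without progression would be censored at discontinuation even in an all-treated PFS analysis, so her exclusion acts mainly on ORR.

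Third, efficacy is secondary, called preliminary in Section 14.1, and carries no hypothesis or threshold. The RP2D rests on the DLT rate, dose cohorts are only summarised descriptively, and the safety set is all treated. In addition, 25% against 20% is small beside intervals spanning more than 40 percentage points. These points lower the priority, but imprecision does not justify a denominator that errs in one direction.

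Finally, the Synopsis already plans an all-treated tabulation of response. That helps only if Section 14 is changed to agree with it.

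**Conclusion.** The point holds. Sections 9.1.2, 14.5 and 14.5.5 select the efficacy set on a post-baseline outcome and contradict the Synopsis. The expected direction is upward for ORR, the stable disease rate and PFS.

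The size cannot be fixed from the documents. For ORR and the stable disease rate it is at most a factor of 1/(1-q), for example 1.25 if 20% do not complete and none of them has a documented response. For PFS, under the exponential assumption and true medians of 8 to 26 weeks, it is about 1.4 to 5.5 weeks if a quarter to a half of the early events are excluded. The 12-week shift is an upper bound requiring every early event to prevent completion, which the scan schedule and treatment past progression make implausible as a typical case.

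This should be fixed before analysis, but it leaves the primary safety objective and the choice of RP2D untouched.

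**What to change.** - In Sections 14.5 and 14.5.5, define the efficacy population as all subjects who receive at least one dose, in line with the Synopsis, and align Section 9.1.2.
- Count subjects with no post-baseline assessment as non-responders for ORR and as not achieving disease control in the stable disease rate.
- Analyse PFS from first infusion in all treated subjects, with deaths as events. Section 13.7.1 already requires deaths from any cause to be reported through the surveillance period. Word the censoring sentence so that it does not override a reported death.
- Keep cycle-1 completers as a labelled supplementary set, and state whether completing a cycle means four infusions or reaching Week 12.

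The change is to wording and needs no new data collection. The cost is less favourable ORR and PFS figures. There is also a limitation to report. Table 5 schedules no imaging during follow-up, so subjects who stop without progression, and for whom no death is reported, are censored at discontinuation. That censoring may be informative, and this should be stated beside the PFS results.

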14.5.1 Subject Disposition

The number and percentage of subjects entering and completing the clinical study will be presented overall and by dose cohort.

14.5.2 Demographic Information and Baseline Characteristics

Demographic and baseline characteristic will be descriptively summarized by study phase and dose.

14.5.3 Protocol Deviation

Protocol deviations will be listed by subject.

14.5.4 Analysis of Safety

All subjects who receive at least 1 dose of study treatment will be included in the safety analyses.

All AEs will be summarized by subject, dose, and prior recurrence history (aggressive [recurrence within 2 years]/non-aggressive).

The CTCAE v 4.03 will be used for AE grading (Grades 1 to 4). AEs will be classified using the Medical Dictionary for Regulatory Activities (MedDRA®) coding system.

The overall incidence of AEs will be summarized and classified by body system and ADXS11-001 dose. An AE will be summarized if the onset date occurs any time during study treatment or up to 30 days after the last dose of study treatment; or, if it occurs prior to Day 1 and worsens while on therapy. The type, incidence, severity, and causality of each AE, the duration of the event, and any required treatment interventions will be tabulated.

Physical examination results will be presented in the subject data listings. Vital sign measurements will be summarized at each infusion using descriptive statistics. The incidence of clinically significant laboratory abnormalities will be presented, and laboratory data will be summarized at each infusion by the CTCAE v 4.03 toxicity

grades. Laboratory data will be presented for subjects having Grade 3 or 4 changes from baseline.

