Doses will be escalated in the standard 3 + 3 fashion, starting with 5 x 10^9 colony forming units (CFU) to a maximum dose level of 1 x 10^{10} CFU. Dose cohorts of 3 subjects each will be treated. In the absence of dose-limiting toxicity (DLT) as defined in Section 6.1 Dose Limiting Toxicity assessed during the first treatment cycle, the dose will be escalated to the next dose level for the next 3 subjects. If DLT is seen in 1 of 3 subjects, another 3 subjects will be treated at that same dose. If DLT is seen in 2 of 6 subjects, then that dose level will be considered maximum tolerated dose (MTD) and the previous dose level will be selected as the recommended Phase 2 dose (RP2D). The RP2D will be selected based on an observed DLT rate of < 33%.

Treatment cycles can be repeated at the RP2D (or less) for an individual subject until a discontinuation criterion is met. Discontinuation criteria include documented disease progression, intolerable side effects not resolved with dose reduction or change in premedications or the subject completes 1 cycle of treatment post observation of complete response (CR) per RECIST 1.1 and immune-related RECIST criteria (irCR).

Sponsor:	Name of Finished Product:	Type of Treatment:
Advaxis, Inc.	ADXS11-001	Lm-LLO Immunotherapy

Further assessment of the RP2D level may be explored in an expansion cohort in subjects with persistent, metastatic, or recurrent carcinoma of the cervix who have failed conventional therapy to evaluate the safety and clinical activity of ADXS11-001. Treatment will continue for each subject until a discontinuation criterion is met. The end of treatment will be defined as 1 year after the last subject's first treatment or until that subject has met a discontinuation criterion. All subjects will be followed for adverse events (AEs) and serious adverse events (SAEs) from the time written informed consent is signed through the completion of the *Lm* surveillance period.

Safety will be assessed by comparing treatment-related AEs, changes in physical examinations, vital sign measurements, laboratory abnormalities and *Lm* surveillance monitoring.

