- Documentation of non-cancer surgeries, including, but not limited to artificial (prosthetic) joints, implants and/or devices, such as port/stent implant placed prior to study enrollment.
- Documentation of any on-study non-drug treatment and surgical procedures, including but not limited to artificial (prosthetic) joints, implants and/or devices.
- The pretreatment prophylactic regimen will be administered prior to and completed at least before each ADXS11-001 infusion.
- ADXS11-001 may be administered ± 7 days within Day 1 of each scheduled infusion. ADXS11-001 should not be administered less than 2 weeks apart without Sponsor approval.
- All subjects will receive a 7-day course of oral antibiotic therapy starting 72 hours after administration of ADXS11-001. All subjects will also receive an additional 6-month oral antibiotic course to be initiated 72 hours following the last dose of study treatment or upon discontinuation of study treatment.
- AEs and SAEs will be assessed from the time Informed Consent is obtained through the completion of the *Lm* surveillance period. All AE/SAEs will be followed through resolution. All AEs/SAEs experienced during this period must be recorded on the eCRF.
- Physical Examinations are to be completed prior to the ADXS11-001 administration to confirm safety criteria for study drug administration are met. PEs may be performed more frequently, as clinically indicated. Height will be measured at screening only. Weight will be collected prior to each ADXS11-001 infusion.
- Monitor vital signs every following the completion of every ADXS11-001 infusion.
- All laboratory procedures are to be completed and assessed by the investigator within 3 days prior to the administration of study treatment to confirm safety criteria for study treatment administration are met.
- 17 Coagulation profile will be assessed at screening only.
- A pregnancy tests must be performed within 72 hours prior to each ADXS11-001 infusion for female subjects of childbearing potential or less than 1 year postmenopausal. If the urine test is positive or cannot be confirmed as negative, a serum pregnancy test will be required.
- 19 Lm surveillance will include routine monitoring of CBC, CMP (including CRP, ESR) and blood cultures. Following completion of study treatment all assessments will be performed every 3 months (±2 weeks) for 3 years beginning 3 months after the subject's last dose of study treatment.

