11.5.2 Management and Surveillance of Listeria during Study Participation

In the event a subject experiences a persistent fever lasting 72 hours after receiving study treatment then the oral antibiotic regimen will be replaced by broad spectrum IV antibiotic treatment. If symptoms consistent with sepsis occur close to ADXS11-001 administration or at any time after ADXS11-001 administration, immediate medical attention must be sought. A microbial culture will be taken to identify the agent of sepsis and antibiotic sensitivity testing should be performed to confirm susceptibility. An infectious disease consult should be obtained for further management of these subjects.

All subjects will receive a 6-month course of an oral antibiotic regimen as a prophylactic measure following the completion of the last dose of ADXS11-001 treatment or at the time of study discontinuation. This additional safety measure is intended to eradicate *Lm* from the body.

Lm surveillance monitoring will also be initiated following the completion of the last dose of ADXS11-001 treatment or at the time of study discontinuation. This monitoring

will include obtaining a blood sample for CBC, comprehensive metabolic panel (CMP), including CRP and ESR, and blood cultures for the detection of *Listeria*. Testing will be performed on all subjects who have received at least 1 dose of ADXS11-001 and occur every 3 months (±2 weeks) for 3 years.

Should a diagnosis of listeriosis be made at any point after treatment with ADXS11-001 and the 6-month course of oral antibiotics are completed, immediate and intensive IV antibiotic treatment (ampicillin +/- gentamycin or other IV antibiotic regimen as indicated) is required. An infectious disease consult should be obtained. Based on each individual subject's case and at the discretion of the treating physician, the removal of any foreign medical object that has been present since treatment with ADXS11-001 was initiated may be warranted. It is extremely important that the Investigator, his/her research staff, other healthcare providers involved in the care of the subject as well as each subject participating in this study are educated and made aware of the signs and symptoms of listeriosis and the potential for delayed listeremia/listeriosis. Educational materials for the Investigator, research staff, health care providers and subjects will be prepared and educational training performed.

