13.6 Evaluating Adverse Events

An Investigator who is a qualified physician will evaluate all AEs according to the CTCAE v 4.03 (See Table 12). Any AE that changes CTCAE grade over the course of a given episode will have each change of grade recorded on the AE case report forms/worksheets. All AEs regardless of CTCAE grade must also be evaluated for seriousness.

Table 12 Evaluating Adverse Events

V4.03 CTCAE Grading	Grade 1	Mild; asymptomatic or mid symptoms; clinical or diagnostic observations only; intervention not indicated.			
	Grade 2	Moderate; minimal, local or noninvasive intervention indicated; limiting age-appropriate instrumental ADL.			
	Grade 3	Severe or medically significant but not immediately life-threatening; hospitalization or prolongation or hospitalization indicated; disabling; limiting self-care ADL.			
	Grade 4	Life threatening consequences; urgent intervention indicated.			
	Grade 5	Death related to AE			
Seriousness	A serious adv	erse event is any adverse event occurring at any dose or during any use of Advaxis product that:			
	†Results in de	eath; or			
	†Is life threatening; or places the subject, in the view of the investigator, at immediate risk of death from the event as it occurred (Note: This does not include an adverse event that, had it occurred in a more severe form, might have caused death.); or				
	†Results in a persistent or significant disability/incapacity (substantial disruption of one's ability to conduct normal life functions); or				
	†Results in or prolongs an existing inpatient hospitalization (hospitalization is defined as an inpatient admission, regardless of length of stay, even if the hospitalization is a precautionary measure for continued observation. (Note: Hospitalization [including hospitalization for an elective procedure] for a preexisting condition which has not worsened does not constitute a serious adverse event.); or				
	†Is a congenital anomaly/birth defect (in offspring of subject taking the product regardless of time to diagnosis);or				
	Is a new cancer; (that is not a condition of the study) or				
	Is an overdose (whether accidental or intentional). Any adverse event associated with an overdose is considered a serious adverse event. An overdose that is not associated with an adverse event is considered a non-serious event of clinical interest and must be reported within 24 hours.				

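### The AE summary rule stops 30 days after the last dose and no surveillance analysis is specified, so late-onset listeria infection falls outside the AE incidence tables; the grading text also omits Grade 5

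*Combined protocol and SAP*

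**What the plan says.** The analysis rule is in Section 14.5.4: "An AE will be summarized if the onset date occurs any time during study treatment or up to 30 days after the last dose". The only other route into the summary is an event that began before Day 1 and worsened on therapy. For laboratory results, "laboratory data will be summarized at each infusion by the CTCAE v 4.03 toxicity" grades. For severity, "The CTCAE v 4.03 will be used for AE grading (Grades 1 to 4").

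The same section also contains text with no time limit. It says "All AEs will be summarized by subject, dose, and prior recurrence history", which the Synopsis repeats in substance, and it promises the incidence of laboratory abnormalities judged clinically significant.

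Collection runs much longer. A footnote to Table 5 says "AEs and SAEs will be assessed from the time Informed Consent is obtained through the completion of the" Lm surveillance period, and Sections 8.1, 13.2 and 13.7.1 agree. The Synopsis makes surveillance part of the safety assessment: "Safety will be assessed by comparing treatment-related AEs, changes in physical examinations, vital sign measurements, laboratory abnormalities and" Lm surveillance monitoring. It also lists surveillance blood cultures among the safety criteria. Section 11.5.2 asks that staff and subjects be taught about "the potential for delayed listeremia/listeriosis". Table 12 in Section 13.6 defines Grade 5 as "Death related to AE".

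**The concern.** Safety and tolerability is the sole primary objective (Section 4.1), and 3 years of follow-up are imposed on every treated subject largely to find late listeria infection. The only explicit inclusion rule for the AE tables closes before the first scheduled surveillance test. Nothing in Section 14 names a table for surveillance cultures, CRP and ESR, listeriosis or other post-treatment events.

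If the rule is followed, a late infection could appear in a listing or an SAE report yet be absent from the incidence tables by dose. Nor would a reader of those tables know how many subjects were still being watched, and therefore how much weight a count of zero could bear. The grading text raises a smaller question: how a fatal event is to be shown when severity is tabulated.

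**Working it through.** There is no stated sample size or power figure to reproduce here, because the analysis is descriptive. The check sets the analysis window against the collection period.

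**Inputs**
- AE summary window: 30 days after the last dose (Section 14.5.4).
- AE and SAE collection: consent to the end of the 3-year surveillance (Table 5 footnote; Sections 8.1, 13.2 and 13.7.1).
- Surveillance tests: three-monthly for 3 years, 2 weeks' tolerance either way, the first at 3 months after the last dose (Table 5 footnote).
- Post-treatment antibiotic course: 6 months, starting about 72 hours after the last dose (Section 8.1).
- Conversion assumed: 1 month = 365.25/12 = 30.44 days.

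**Arithmetic**
- Scheduled tests: 36/3 = 12.
- First test, nominal: 3 × 30.44 = day 91. Earliest permitted: 91 − 14 = day 77.
- Scheduled tests by day 30: 0 of 12, since 77 > 30.
- Length of surveillance: 3 × 365.25 = 1,096 days. Share inside the window: 30/1,096 = 2.7%.
- Antibiotic course: from about day 3 to about 3 + 6 × 30.44 = day 186. From about day 3 on, the window therefore lies wholly within the antibiotic course.

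**What the rule does to each kind of event**

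| Event | In the AE summary under the 30-day rule? |
|---|---|
| Listeria infection, onset by day 30 | Yes, even if confirmed later, because the rule turns on onset |
| Listeria infection, onset after day 30 | No |
| Fatal AE, onset by day 30 | Yes, for type, incidence and causality; no severity category |
| Fatal AE, onset after day 30 | No, because of the window and not because of the grade |

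**Competing text.** If the untimed sentence on all AEs governs, late events are summarized and the 30-day sentence has no effect. If the 30-day sentence governs, they are not. Section 14.5.4 does not say which prevails. For laboratory data, the summary by grade is tied to infusions and so cannot include surveillance visits. The sentence on clinically significant abnormalities has no time limit. Table 13 lists surveillance cultures, CRP and ESR as laboratory tests, and Section 13.9 sends surveillance results to the laboratory and AE pages of the eCRF. A positive culture could therefore be read into that presentation, but no text says so.

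**If the gap is closed.** Extending coverage to the end of surveillance moves the limit from day 30 to about day 1,096 and brings in all 12 nominal test dates.

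**The case against.** The best defence is that a 30-day treatment-emergent window is ordinary practice and nothing is lost. Late events are recorded, serious ones are reported within 24 hours throughout surveillance (Section 13.7.1), and data listings are planned (Section 14.1). In a small descriptive Phase 1 trial, one case of listeriosis would be visible in a listing. No dose decision depends on the window, because DLTs are assessed in the first 28 days. The untimed sentences in Section 14.5.4 might also be read as covering late events.

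Most of this stands as fact, and it is why the 30-day table should stay. It does not close the gap. The planned listings are generic, and a listing gives neither a rate by dose nor a denominator. Section 3.1 puts median survival in this population below 1 year, so many subjects may not reach the later tests. The number still under surveillance is then essential to reading any count. The untimed sentences turn the defect partly into a contradiction, which still needs resolving.

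Some stronger readings are tempting but unsupported:
- *Fatal AEs are excluded.* They are not. Inclusion depends on onset date, and Section 14.5.4 contains no exclusion by grade.
- *The tables would show zero late infections whatever happened.* That takes the 30-day sentence as certain to prevail and ignores the competing text.
- *The section was overlooked when surveillance was added.* The readable part of the change log ends at Section 12 and cannot show this.
- *Binomial limits measure the harm.* With 0 of 15 subjects the exact upper 95% limit is 21.8%, but that reflects sample size and is the same under any AE window.

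**Conclusion.** The concern holds for the AE inclusion rule. As written, it leaves a listeria infection with onset after day 30 out of the AE incidence tables, although such events are collected for 3 years and belong to the primary objective. In size, 0 of 12 scheduled surveillance tests and 2.7% of the surveillance calendar fall inside the window. The percentage is a share of days, not of events or risk, and it presumes full 3-year follow-up. The test count rests on the Table 5 footnote that starts testing 3 months after the last dose.

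Two qualifications apply. Part of the defect is an internal conflict with the untimed text on all AEs and on laboratory abnormalities, so omission is what the explicit rule produces and not the only possible reading. The grading point is narrower: Section 14.5.4 disagrees with Table 12, so a fatal AE inside the window is counted without a severity category. No data are lost and dose escalation is unaffected.

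**What to change.** In Section 14.5.4:

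1. Keep the 30-day treatment-emergent table, and state that the 30-day rule applies to that table only. This also resolves the conflict with the untimed sentence.
2. Add a table by dose covering Day 31 after the last dose to the end of surveillance. Give the number and percentage of subjects with any AE or SAE, with listeriosis, and with a positive Lm culture, together with the number still under surveillance.
3. Change the AE grading text to Grades 1 to 5, in line with Table 12.

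Exact confidence intervals and by-visit summaries of CRP and ESR would be useful but are optional; the defect is cured without them.

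The cost is analysis wording and a few extra tables. The data are already collected, and no visit, assessment or subject is added. The tables are best defined before late events are known, so that their form does not depend on what was seen.
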